Valve hemodynamics are to be gathered from the view giving the best signal. If the view used is different from those listed in the progressions noted in the previous section, then note the view used for either pressure or regurgitation measurement.

Provide the hemodynamic data requested on the form from the view that provides the best signal.

Subaortic diameter measurement should be made from the trailing edge of the left septal echo to the leading edge of the anterior mitral leaflet echo. If severe left ventricular hypertrophy or bowing of the anterior mitral leaflet exist, this measure should not be made and the space should be noted as unavailable on the CRF.

E. Reoperation and/or Explant Procedures

Whenever a valve reoperation occurs whether or not as a result of one of the complications described in Section C above complete and return CRF 5.

Explants are requested at autopsy whenever practical. Reoperative explants may also occur. Return of explanted valves within the study is required.

Specific explant analysis requirements are included in this plan. Explanted mechanical valve prosthesis refers to a study valve that has been removed from the patient at reoperation or autopsy. The recommended procedures have been developed to ensure accuracy, consistency and completeness of the analysis of explanted valves. This section outlines in detail the procedures for explanting, recording data and returning the explanted valves.

Explanting the Valve

When explanting a valve at reoperation or autopsy:

- Inspect the mechanical valve prosthesis prior to removal including the condition of the annulus for evidence of dysfunction such as thrombi, paravalvular leak, vegetations, pannus overgrowth. Culture of pertinent areas of the valve when appropriate is mandatory.
- 2) Examine the lining of the chambers of the heart, both proximal and distal to the valve for possible jet lesions or endocardial fibrosis.
- 3) Special attention should be paid to the possibility of extrinsic interference with the valve function, particularly by retained mitral valve leaflet tissue or sutures.
- 4) If possible, photograph the mechanical valve prosthesis *in situ*. For valves obtained at autopsy, photograph both the inflow and outflow aspects.
- 5) DO NOT rinse the valve.
- 6) Request an explant kit from the sponsor and place the valve in the jar provided in the explant kit.
- 7) If no explant kit is available, place the valve in either 1% glutaraldehyde solution or 10% buffered formalin until a kit is obtained.
- 8) Record observations on CRF5 in the appropriate locations.

Data and Shipping Requirements

To send the data and return the valve to study sponsor:

- 1) Attach a copy of the reoperative or autopsy report to the appropriate CRF5.
- 2) Attach any *in situ* photographs to CRF5.
- 3) Ship the valve as instructed in the explant kit, clearly marked as an explant, and inform the monitor by telephone or telefax of its shipment.
- 4) Notify your clinical research monitor if the valve cannot be returned.
- 5) If the valve is examined by a pathologist at the hospital where it was explanted, send that report to the monitor as well.

Each returned heart valve received by the sponsor (or monitor) will be tracked and analysis information compiled and stored. Each explant will be analyzed by the independent study pathologist and his/her report will be provided to the investigator and monitor.

F. Adverse Events

If a test group patient suffers a thrombotic event during the trial, he/she will be removed from the cohort and returned to standard Coumadin therapy. If a test group patient suffers a bleeding event during the trial, he/she may continue with the LD therapy regime or may be removed from the study depending upon the principal investigator's clinical judgment. In any case such patients shall be followed and remain in the test group for analysis purposes based on an intent-to-treat classification.

G. Study review

At least 3 independent advisors, including at least one each from cardiology, cardiac surgery and statistics, will act as the Data Safety Monitoring Committee. The Committee will examine reports of adverse events and their rates of occurrence on a regular basis, no less often than annually. The Committee will also review the occurrence of any thrombotic event as early as feasible after it occurs. The Committee shall have the power and authority to direct changes in, or termination of, the study. The study shall be terminated, if at anytime, while patients are maintained on LD therapy, the rates of thrombotic and bleeding events exceed either the rate in the control group, the expected rate from the sample size calculation, or twice the aggregate rate of such events reported for other bileaflet valves in the peer reviewed literature, as determined by meta-analysis.

Changes to the plan can only occur with concurrence of the Data Safety Monitoring Committee and ethics committees.

The committee shall initially consist of:

1. [name]

Professor of Surgery Beth Israel Deaconess Hospital Harvard University Boston, Massachusetts

2. [name]

Professor of Cardiology Hopital Laval, Ste-Foy, Quebec, Canada 3. [name] Professor of Hematology McMaster University Hamilton, Ontario, Canada 4. [name]. Adjunct Faculty, Biostatistics Johns Hopkins University Baltimore, Maryland

H. Data Analysis

Data will be analyzed using Kaplan-Meier life tables and linearized rates. Although randomization does not occur until month 3, early postoperative data (\leq 3 months postoperative) will be analyzed to examine potential differences between test and control groups using regular percentage comparisons. Data will be stratified by risk factors including age and others as appropriate. Data forms will be completed preoperatively, operatively and at each follow-up. This can be done on paper or electronically at the mutual choice of the center and the study monitor.

Case Report Forms -

Example Case Report Forms are provided in Appendix A. A forms notebook or electronic database for each patient will be provided by the sponsor. The notebook is designed to make keeping the records for the study more organized and to reduce the potential for mixing up data. An electronic database may also be used for this purpose. Extra forms will be provided on request, or as needed.

I. Reports

Summary reports of the study shall be produced annually by the sponsor and monitor, and be provided to each investigator, Data Safety Monitoring Committee member and ethics committee chairperson.

IV. Device Description and Risk Analysis

The On-X prosthesis is a bileaflet mechanical heart valve prosthesis. The housing consists of On-X pyrolytic carbon coating on a graphite substrate.

Two radiopaque leaflets are constrained by pivots in the housing walls. The leaflets are On-X pyrolytic carbon deposited on a graphite substrate which is mixed with 10 weight % tungsten to allow for radiographic visualization. In the closed position, the occluders rest at 40° within the valve orifice. The valve design permits maximum leaflet opening angles of 90° from the plane of the housing, a position that follows flow. The pivot design includes features that enhance and ensure closure response to reverse flow and opening response to forward flow.

The rotatable sewing ring is made from polytetrafluoroethylene (PTFE) fabric attached to the valve housing by means of titanium retaining rings and 5-0 suture material. The

retaining rings positively attach the sewing ring to the valve housing by straddling a flange on the housing OD. They also provide the means for radiographic visualization and identification. There are no coatings or treatments on the fabric, although black orientation marks are included on the ring fabric. The sewing rings are supra-annular and allow the tissue annulus to abut the pyrolytic carbon housing directly, except in sizes larger than 25 mm, where the sewing rings become intra-annular to allow the 25 mm housing (largest size made) to fit properly into larger tissue annuli.

Valves are packaged on a valve holder with a separately packaged, removable handle to facilitate insertion and in situ orientation, and to provide protection during shipment and handling. The package is designed for shipment protection as well as handling ease. Valves are surgically clean and have been sterilized. The instructions for use packaged with the valve describe the handling of the valve during surgery in detail. Adhere to all instructions, warnings and precautions in the labeling.

A review of the literature on Coumadin anticoagulation of mechanical heart valve prostheses is inconclusive on the preferable therapy for various valves. Various groups have struggled with the lack of information on the subject of anticoagulation; yet have crafted recommendations based on information available. These include the ACCP⁽³⁾ and AHA/ACC⁽⁴⁾ recommendations. Butchart⁽⁵⁾ in a review of embolism in prosthetic heart valves concluded that valves vary in susceptibility to thrombosis due to subtle design differences, that optimal INR range is often uncertain, and that further research is needed.

Many studies of various mechanical valves have attempted to examine low intensity Coumadin therapy, Coumadin plus aspirin, aspirin alone and even no anticoagulation. These studies have had mixed results. Horstkotte ⁽⁶⁾ suggested that INR levels of 3.0 to 4.5 are too high for the St. Jude valve, but that a prospective trial is needed to show the proper level. Cannegieter ⁽⁷⁾ in the first detailed study of optimum anticoagulation suggested the target of 3.0 to 4.5 initially.

Others have studied and suggested lower INR targets ⁽⁸⁻¹²⁾ in the range of 2.0 to 3.0. These studies resulted in the lower recommendation of ACCP and ACC. Still other groups have examined lower Coumadin in combination with antiplatelet agents, such as aspirin or dipyridamole. Starting with the work of Turpie, et al ⁽¹³⁾ various groups have shown a benefit of adding aspirin or dipyridamole, to Coumadin ⁽¹⁴⁻¹⁵⁾. But some mixed results indicating a possible increase in bleeding occurred with addition of aspirin ⁽¹⁶⁻¹⁷⁾. Three separate meta-analyses ⁽¹⁸⁻²⁰⁾ support the addition of lowdose aspirin or dipyridamole to Coumadin.

Another strategy for reducing thrombotic and bleeding events from Coumadin therapy is to control the therapy better with clinic or home monitoring. These studies have uniformly shown better results with better control ⁽²¹⁻²³⁾. Yet still bleeding and thrombosis rates are considered suboptimal for mechanical valves, even though a background rate for these events exists that becomes about 2% per year at 80 years old ⁽²⁴⁾.

As mechanical valves have long been known for their durability, they have also been thought to require long-term Coumadin anticoagulation to prevent thrombotic events. This requirement subjects patients to an increased risk of bleeding events and has been the major shortcoming in the performance of mechanical valves. It is, therefore, desirable to reduce or eliminate Coumadin anticoagulation.

The valve selected for this trial must also be shown to perform better than existing mechanical valves in terms of adverse events and other surrogate endpoints that indicate possible reduction of events based on the effects of valve design. These endpoints include adverse event rates, (especially in relation to the degree of anticoagulation actually achieved in a study), hemodynamics and hemolysis.

The On-X aortic valve has been shown to achieve low adverse event rates ^[25,26], especially in the face of sporadic anticoagulation ^[27]. This is true also when compared to a similar contemporary study ^[28]. The hemodynamics of the valve are superior to other mechanical valves ^[26,29] indicating a reduction in turbulence which can effect blood damage and thrombotic events. The valve also produces very little hemolysis in the aortic or mitral position ^[30], which also indicates a potential for reduced thrombotic complications.

A study of the valve in sheep in a model designed to predict resistance to thrombosis, performed by Flameng ⁽³¹⁾, found that the On-X valve statistically outperformed both the SJM and CMI valves. The first thrombosis of an On-X valve occurred at 6 weeks compared to 2 weeks for the others. Additionally, 2 of 6 test valves survived the test without thrombosis compared to 0 of 7 for the others.

In an ongoing clinical trial in South Africa ⁽³²⁾, 200 On-X valves have been implanted with 100% follow-up out to about 3 years. About 40% of these patients are not anticoagulated due to the social conditions in South Africa, yet there has been only one thrombosis event in the mitral position in the study. Given the valve's clinical performance to date, it is an ideal candidate for a study using lower dose Coumadin.

V. Monitoring Procedures

The monitor of the study shall be a professional staff member of the Clinical Studies Department of the sponsor. Monitoring of the clinical trial will be a continuous process to ensure that high quality data are obtained through compliance with the investigational plan. Case report forms or electronic data will be reviewed for accuracy, completeness, and conformity with requirements. Particular attention will be paid to complication reporting. Frequent communication will be maintained with each clinical center to keep both the center and the sponsor informed and aware of the clinical trial progress.

On-site monitoring of all study centers will occur at least annually to ensure continued acceptability of the center by assessing compliance to the investigational plan., adherence to data collection procedures, verification of the accuracy of submitted clinical data to the patient's source documents, maintenance of clinical trial records, verification of informed consent, and verification of control of test articles. Reports of each center's audits will be provided to the investigator and sponsor, and if necessary, appropriate corrective action will be taken to ensure compliance to the investigation plan.

Preinvestigation Visit:

Preinvestigation visits will be conducted by the clinical trial monitor to review the investigational plan and discuss the report of previous investigations with the investigator and staff to assure that they:

- Understand the investigation of the device and the requirements for its accountability.
- Understand the nature of the investigational plan including record, reports and recruitment of patients.
- Understand the requirement for an adequate, well controlled clinical trial.
- Understand and accept the obligation to conduct the clinical investigation in accordance with applicable national regulations.
- Understand and accept the obligation to obtain Ethics Committee or Institutional Review Board (IRB) review and approval before the clinical trial may be initiated, ensure continuing review of the trail by the Ethics Committee or IRB and keep the sponsor informed of any actions by the Ethics Committee or IRB that concern the clinical trial.
- Have access to an adequate number of suitable patients to conduct the investigation.
- Have adequate facilities and staffing to conduct the investigation.
- Have sufficient time from other obligations to fulfill the responsibilities of the investigation.

Particular attention will be given complication reporting.

Annual Center Visit and Audit:

Following the preinvestigation visit, on-site monitoring visits will be conducted at least annually.

On-site monitoring visits will assess the progress of the clinical trial and identify any concerns that result from device performance and review of the investigator's clinical trial records, study management documents and patient consent forms. This review includes adherence to the investigational plan, Ethics Committee or IRB review of the clinical trial and its progress and maintenance of records and reports.

To assure the integrity of the clinical trial data, individual patient records and other source documents are compared to reports from the investigator to determine that:

- The information recorded in the case report forms and/or reports is accurate, complete and legible.
- There are no omissions in the case report forms of specific data (e.g., development of an intercurrent illness)
- Missing follow-up visits are documented in the reports.
- Patients failing to complete the clinical trial and the reason for failure are noted in the reports.
- Informed consent has been documented.

A record of the monitor's findings will be maintained by the sponsor and investigator and will contain the following information:

- The date(s) of the visit.
- The name(s) of the monitor(s) who conducted the visit.
- The name(s) and address of the investigator(s) and other center staff who were visited.
- A statement of the findings, conclusions and any actions taken to correct deficiencies observed during the audit.

Resolution of concerns and completion of assigned tasks will be documented by the monitor.

Interim Visits:

Interim visits to the study centers will be conducted as deemed to be necessary, typically only when circumstances require additional training or assistance as determined by the monitor.

Final Center Visit:

A final visit to the study center may be made by the monitor, if necessary. Any ongoing responsibilities that will continue after the final visit will be discussed with the investigator and the study center coordinator. A final monitoring report, which includes device inventory verification and disposition of unused devices, will be prepared by the monitor.

Regular Reports:

The monitor will provide regular at least quarterly summary reports of the clinical investigation to all investigators and the sponsor. The contents of these reports will be determined by the monitor and sponsor jointly.

The sponsor or monitor will provide reports to each investigator based on individual requests for data. Each investigator will also get at least a quarterly update of the required activities for the study at his/her center.

VI. Legal/Ethical Considerations

The study will be conducted under the rules of the local country or the Declaration of Helsinki whichever provides more patient protection. Where governmental approval is required (FDA, competent authority or Health Canada), it will be obtained prior to starting the study at any center in such country. All centers will have the approval of their local ethics committee before beginning patient enrollment. All patients will be given adequate written informed consent. The patient must agree to, and understand, the drug therapy regime and the follow-up requirements. Informed consent shall include all elements of information required by international standards, and shall notify the patient that data will be shared with government regulatory bodies as needed. See the example in Appendix C.

Sponsors must be able to verify to regulatory agencies, e.g., the Food and Drug Administration, that this clinical investigation has been conducted in accordance with ethical principles. The Investigational Device Exemption (IDE) regulation applies to the United States. At each center investigators are required to:

- Obtain informed consent from patients involved in the clinical trial
- Obtain Institutional Review Board approval prior to starting the clinical trial at their institution.

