Test Group III, (regardless of risk) – First 3-months postoperation, Coumadin at an INR target of 2.5 to 3.5 with 81 mg/day (75 mg/day in Italy) aspirin will be used. After 3-months, Coumadin dose will be reduced to an INR target of 2.0 to 2.5 with 81 mg/day (75 mg/day in Italy) of aspirin continued.

Control Group – Postoperatively Coumadin with an INR target on 2.5 to 3.5 with 81 mg/day (75 mg/day in Italy) aspirin throughout the study.

D. Sample Size

A sample size estimate was conducted based on FDA OPC criteria^[1]. The study is expected to test the safety of low dose (LD) therapy for anticoagulant therapy in On-X valve patients with LD therapy consisting of the use of Coumadin in combination with aspirin or the use of antiplatelet therapy alone. This study is designed as a non-inferiority study requiring only that LD therapy is not inferior to standard

Coumadin/aspirin treatment. Testing the superiority of LD therapy with adverse event rates as low as expected would require exposure of a prohibitively large patient group. It was necessary for the sample size calculation to assume an acceptable event rate for the primary endpoints of thromboembolism, thrombosis and bleeding events derived by summing the FDA OPC's. The incident rate of the sum of these three events needs to be at least as low as the OPC sum, 7.3%. Table 1 gives the resulting sample size requirements based on a variety of outcomes.

The number of patients to be enrolled in the clinical trial is based first on the ability to show that linearized adverse event rates for the primary endpoints in the test groups are not inferior to the corresponding control groups and second on the ability to show that all valve related adverse event rates in the test groups do not equal or exceed 2 times the rates determined to be acceptable for mechanical valves.

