For the first criterion above, the test group will need to have less than 6%/ptyr cumulative rate of the three events for the study to reach significance with a randomized patient population of between 150 and 250 per group followed for between 5 and 6.7 years at a statistical power of 80% with type I error of 0.05 and a maximum allowable difference between groups of 1.5%. It is expected that each of 50 centers will be able to enroll an average of 30 patients into the study balanced to provide adequate population in each sub-group, providing sufficient patient-years to test the hypothesis, which under the above conditions is around 1000 as shown in Table 1. Thus the study has 200 patients per group in AVR high risk with an average of 5 years of follow-up, or alternatively 150 patients in AVR low risk averaging 6.7 years of follow-up and and up to 250 MVR averaging 4 years of follow-up, providing the approximately 1000 patient-years per group estimated to meet hypothesis.

For the second criterion above, the established rates are the objective performance criteria (OPC) given in the FDA guidance document ⁽¹⁾. The adverse event rates for which OPCs are established include the primary endpoints of thrombosis, thromboembolism and bleeding and the secondary endpoints of paravalvular leak and endocarditis as listed below:

% per valve year (R_A)
0.8
3.0
3.5
1.5
1.2
1.2

In the comparison to OPCs for each adverse event, the null hypothesis being tested is that the true adverse event rate for each test group is equal to or greater than twice the acceptable rate. Rejecting the null hypothesis would conclude that the rate for the test groups is less than two times the acceptable rate. The null and alternative hypotheses can be written as:

Null hypothesis:	$R \ge 2R_A$
Alternative hypothesis:	$R < 2R_A$

Table 1

Sample Size Estimation for On-X Trial LD Therapy vs. Control

The sample size estimation is based on one-sided proportion test, which tests that the incidence rate of thrombosis, thromboembolism and hemorrhage in the LD therapy groups are at least as low as the control groups.

				Maximum Allowable	
Type I Error	Statistical	Expected	Expected	Difference	Needed
(One-sided	Power	Proportion	Proportion	between Two Groups	Patient
Test)		In Control	In Low Dose	to Declare Non-inferiority	Years
		Group	Group		
0.05	80%	7.3%	4.5%	2.0%	309
			5.0%	2.0%	398
			6.0%	2.0%	719
			7.3%	2.0%	2112
			4.5%	1.5%	381
			5.0%	1.5%	504
			6.0%	1.5%	992
			7.3%	1.5%	3739

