4. SAMPLE SIZE CONSIDERATIONS

The study is expected to test the safety of low dose (LD) therapy for anticoagulant therapy in On-X valve patients with LD therapy consisting of the use of Coumadin® in combination with aspirin or the use of antiplatelet therapy alone. The sample size for this study was designed as a non-inferiority study requiring only that LD therapy is not inferior to standard Coumadin®/aspirin treatment. It was necessary for the sample size calculation to assume an acceptable event rate for the primary endpoints of thromboembolism, thrombosis and bleeding events derived by summing the FDA OPC's. The incident rate of the sum of these three events needs to be at least as low as the OPC sum, 7.3%.

The test group will need to have less than 6%/ptyr cumulative rate of the three events for the study to reach significance with a patient population of 200 per group followed for 5 years at a statistical power of 80% with type I error of 0.05 and a maximum allowable difference between groups of 1.5%.

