11. INTERIM ANALYSIS

No interim analyses are planned, but they may occur at the request of the Data Safety Monitoring Committee, or the request of the Principal Investigators and approval of the Sponsor as a result of their annual meeting, or the FDA.

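### The mandatory termination rule stops on any raw excess over control and is left out of the stated 80% power; with five annual looks the chance of concluding non-inferiority at the design rates falls from 78% to 56%

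*Protocol*

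**What the plan says.** The rule is in Protocol III.G: "The study shall be terminated, if at anytime, while patients are maintained on LD therapy, the rates of thrombotic and bleeding events exceed either" any of three comparators. The first two are "the rate in the control group, the expected rate from the sample size calculation"; the third is double the rate for other bileaflet valves from a meta-analysis of published reports. No significance level, confidence limit, minimum event count or minimum exposure is attached. On timing, "The Committee will examine reports of adverse events and their rates of occurrence on a regular basis, no less often than annually", and in addition "The Committee will also review the occurrence of any thrombotic event as early as feasible after it occurs".

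The sample size text describes a single fixed comparison. For the control rate, Protocol II.D says "The incident rate of the sum of these three events needs to be at least as low as the OPC sum, 7.3" (percent). For the test rate, "the test group will need to have less than 6%/ptyr cumulative rate of the three events for the study to reach significance". SAP section 4 repeats the operating characteristics: "a statistical power of 80% with type I error of 0.05 and a maximum allowable difference between groups of 1.5" (percentage points). Table 1 gives 992 patient-years for this case at one-sided 0.05. Neither sample size section mentions the termination rule.

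SAP section 11 says "No interim analyses are planned, but they may occur at the request of the Data Safety Monitoring Committee" and certain other parties. It does not list the committee's rate reviews. That is an omission rather than a contradiction.

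**The concern.** A non-inferiority design with a 1.5-point margin accepts that the test arm may run somewhat above control. The termination rule accepts no excess at all, at any time. Early in follow-up the counts are small. At 200 patient-years per arm the expected counts are 12 on low dose and 14.6 on control, so a regimen that is truly better by the planned amount will often be above control by chance. Applied as written, the rule ends many trials that would have gone on to show non-inferiority, and the stated 80% is then not the power of the design.

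The rule also cannot be applied without further decisions. It does not say:
- whether thrombotic and bleeding rates are pooled or compared separately;
- whether each test/control pair is judged alone or the study as a whole;
- whether the planning rate is 7.3% or 6.0%;
- how often beyond once a year the comparison is made.

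Two committees reading the same sentence could reach opposite decisions on the same data.

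**Working it through.** **Inputs from the documents.** Control 7.3% and low dose 6.0% per patient-year, margin 1.5 points, one-sided 0.05, about 1000 patient-years per group (Protocol II.D and Table 1); 200 patients per group for 5 years (Protocol II.D, SAP 4); at least annual review (Protocol III.G).

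**Assumptions not in the documents.** Poisson events; 200 patient-years per arm per year; five looks at cumulative pooled thrombotic plus bleeding counts; one pair; a stopped trial cannot conclude non-inferiority.

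**Step 1: reproduce the plan's figure.** With binomial variances, n = (1.645 + 0.842)² × (0.060×0.940 + 0.073×0.927) / (0.015 + 0.013)² = 979, against 992 in Table 1, a difference of 1.3%. Power at 1000 patient-years is 80.8% on this scale.

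For linearized (Poisson) rates, SE = √[(0.060 + 0.073)/1000] = 0.01153. Power = Φ(0.028/0.01153 − 1.645) = Φ(0.783) = 78.3%. Exact enumeration gives 78.5%. This is the baseline below.

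**Step 2: the first look.** The expected difference in counts is 12 − 14.6 = −2.6, with SD √26.6 = 5.16. P(low dose count > control count) ≈ 1 − Φ((0.5 + 2.6)/5.16) = 1 − Φ(0.60) = 27%.

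**Step 3: all five looks.** I used an exact recursion on the two cumulative counts, absorbing whenever low dose exceeds control. Otherwise non-inferiority is concluded at 1000 patient-years per arm if the difference + 1.645×SE is below 1.5 points.

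| Look | First stopped here | Success lost here (points) |
|---|---|---|
| 1 | 27.3% | 16.5 |
| 2 | 7.1% | 3.8 |
| 3 | 3.2% | 1.3 |
| 4 | 1.8% | 0.4 |
| 5 | 1.1% | 0.0 |
| Total | 41% | 22 |

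The chance of concluding non-inferiority falls from 78.5% to 56.5%. On the binomial scale, nearest to the plan's own 80%, it falls from 80.9% to 58.3%. Nothing is lost at the last look because 1.645×SE is 1.9 points: success already needs low dose to be observed about 0.4 points below control (1.5 − 1.9).

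**Step 4: other readings, at 6.0% against 7.3%.**

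| Reading | Stopped | Non-inferiority concluded |
|---|---|---|
| Five looks, control trigger only | 41% | 56% |
| 10 looks | 52% | 46% |
| 20 looks | 62% | 37% |
| Annual looks, 200 patients accrued uniformly over 1 to 4 years | 48% to 60% | 50% to 38% |
| 250 patients, 4 years | 37% | 60% |
| 150 patients, 6.7 years | 46% | 52% |
| No look in year 1 | 30% | 66% |
| Three pairs pooled at the looks | 23% | 64% |
| Both event rates must exceed control | 18% | 71% |
| Either event rate suffices | 74% | 26% |
| Control trigger plus planning rate of 7.3% | 49% | 49% |
| Control trigger plus planning rate of 6.0% | 74% | 26% |

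The separate-rate rows assume a 3.8/3.5 split of the 7.3%, taken from the OPCs. The literature-rate trigger is not modelled because the documents give no figure for it.

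**Step 5: other true rates, five looks.** At 7.3% in both arms, 73% of trials stop and success falls from 34% to 22%; power there is low even without the rule. At a true 1.5-point excess (8.8% against 7.3%), false non-inferiority falls from 5.1% to 2.9%.

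**The case against.** **A cautious rule is legitimate.** Test patients receive less anticoagulation than recommended, so an asymmetric safety rule may be deliberate. It makes a positive conclusion no less valid. That stands, and the point here is not that the rule is too strict. It is that the plan states a power which ignores it. The committee's general authority to direct changes offers a route to clarification, but the termination sentence itself is mandatory.

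**56% is one scenario for an undefined rule.** This is fair. If both event types must exceed control, the loss is about 7 points. More looks, staggered accrual or the planning-rate trigger make it larger. A loss appears under every reading tried.

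**The loss depends on the true rate.** This stands. At 5.0%, also listed in Table 1, success with the rule is 80% (96% without); at 4.5% it is 87% (99% without). But 6.0% against 7.3% is the row that supports the 1000 patient-years and the 80%.

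**The SAP's criterion differs.** SAP 6.5 sets two-sided 0.05 by default, and SAP 2.3.1 bases the primary decision on thromboembolism plus major bleeding. With a 1.96 bound the fall is from 68% to 52%. The narrower event set was not modelled.

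**Two of the three test arms no longer enroll.** Protocol II.C says so for both AVR arms, and most of the loss comes at early looks. If looks begin only in year 3, success is 72%. Restating planned power therefore has less practical value for AVR. The mitral arm is still enrolling, and the rule runs for as long as patients remain on low dose.

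**Conclusion.** The concern holds. The stated 80% belongs to a single fixed analysis, and the design as written is not that. At the plan's own design rates, with pooled rates, one pair, five equal annual looks and only the control-rate trigger, the rule stops 41% of trials and cuts the chance of concluding non-inferiority from 78% to 56%. The direction is secure. The exact size is not, because the wording leaves open choices that move the result between 26% and 71%. The harm is to power and to the chance of stopping a regimen that performs as planned, not to the false-positive rate. This should be corrected, though it does not undermine a non-inferiority conclusion from a trial that completes.

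**What to change.** Reconcile Protocol II.D and III.G with SAP sections 4 and 11:
- In III.G, state which planning rate is meant, whether thrombotic and bleeding rates are pooled or separate, whether the rule applies per test/control pair or study-wide, and when the rates are compared.
- Have the sponsor and the monitoring committee decide and pre-specify how chance variation enters the comparison. The choice of threshold is theirs.
- In SAP 11, list the committee's rate reviews, which occur at least once a year.
- In II.D and SAP 4, restate power and the false-stop probability with the rule in place, at 6.0% against 7.3% and at equal rates.

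The cost is wording in four sections and a short calculation. The drawback is that either the published power becomes less favourable or the committee has to agree revised wording.
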